9. RISKS TO SUBJECTS

9.1. Potential Risks: the potential risks include possible breach of confidentiality, risk of

infection, and discomfort from wearing the nose clip or breathing into the mouthpiece.

9.2. Protection Against Risks: The risk of the breach of confidentiality will be reduced by deidentifying data and restricting data access. The risk of infection will be reduced by using a disposable mouthpiece/filter attachment, cleaning the device with a disinfectant between uses, screening subjects for a transmissible respiratory infection, and limiting the testing to individuals vaccinated against COVID-19. Note that IO has been performed in tens of thousands of patients worldwide without adverse effects including infection. The risk of discomfort from wearing the nose clip or breathing into the mouthpiece will be mitigated by allowing subjects to stop testing if they find the brief procedure too uncomfortable.

9.3. Alternatives to participation: non-participation.

10. POTENTIAL BENEFITS TO SUBJECTS

There are no anticipated benefits from participating in this study.

11. COSTS FOR PARTICIPATION

None.

12. PAYMENT FOR PARTICIPATION

- None.

13. SUBJECT WITHDRAWALS

- Subjects can withdraw from study participation at any time and no reason is needed.
- The investigators will otherwise include all data collected from subjects who undergo the proper consent process and who are able to perform the test.

14. PRIVACY AND CONFIDENTIALITY OF SUBJECTS AND RESEARCH DATA

- Each subject will be assigned a unique identifying number (subject ID number). Demographic data and oscillometry data collected will be listed under this unique identifying number on the Excel Sheet saved to the password protected research laptop.
- The subject ID number is otherwise deidentified and will not be linked to the subject in any way. For the purposes of this study, there is no reason to link any patient identifiers to the deidentified subject ID number.
- Consent forms will be maintained in the locked Pulmonary & Critical Care Fellow's Office. Access will be restricted to the co-investigators of this study.

15. DATA / SAMPLE STORAGE FOR FUTURE USE

- Raw oscillometry data will be stored on the device under password protection. Raw oscillometry data on the device and deidentified data saved to the research laptop will be maintained for a maximum of 3 years.
- Once data has been analyzed, the results (which will be deidentified) may be shared at future research conferences.

16. DATA AND SAFETY MONITORING PLAN

The risks from participation in this study are low. Risks are mainly related to breach of confidentiality and infection. The following steps will be taken to ensure data and safety monitoring.

- Definitions:
 - Adverse Event: any untoward medical occurrence related to the study procedure.
 - Serious Adverse Event: Any adverse event resulting in an ED visit, inpatient hospitalization, significant incapacity or death or may require medical or surgical intervention to prevent one of the above outcomes.
- Participants will be asked to contact the investigator if they experience any adverse event that could be related to the study in the days to weeks following the visit.
- If a serious adverse event is identified or reported, a physician who is not a member of the study team will be asked to perform an independent review.
- Adverse events will be reported as required by institutional IRB.

- **DATA ANALYSIS PLAN**
 - Oscillometry measurements before and after deep inspiration will include respiratory system resistance (Rrs), respiratory system reactance (Xrs), and resonant frequency (Fres).
 - We will calculate mean and standard deviation for values obtained before DI (Pre) and after DI (Post). Data will be tested for normal distribution and outlier effects. Differences between Pre and Post will be determined using t-test or ANOVA. Statistical significance will be determined as $p < 0.05$
 - Differences between Pre and Post values will be analyzed after the first twenty (20) subjects have completed testing. If promising trends appear with borderline significance (e.g. $0.05 < p < 0.10$) or if there are a subset of apparent responders, then an additional twenty subjects will be enrolled and analyzed.
 - A formal power and sample size calculation was not performed for this study, which is exploratory in nature.

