4.1. SUBJECT POPULATION

- Up to fifty (50) healthy subjects will be recruited from Mary Parkes Asthma and Allergy Center and the outpatient pulmonary clinics at the University of Rochester Medical Center, and from the Pulmonary and Critical Care Division at the University of Rochester.

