8. STUDY PROCEDURES

- Consent and testing procedure:
 - The investigator performing the test will discuss the protocol with the subject, answer all questions and obtain written consent prior to study enrollment.
 - Subjects will be instructed to refrain from taking deep breaths, sighs, or yawns, for at least 10 minutes prior to testing.
 - Data collected will include oscillometry impedance data (detailed below) and basic demographic information. Demographic information includes age, biological sex, self-reported race, and history of lung disease. All data collected will be stored on the research laptop which will be password protected. Data collected will be deidentified.

February 2022 revision:

- In addition to basic demographic information, subjects will be asked to fill out the following validated questionnaires: The Pittsburgh Vocal Cord Dysfunction Index, Asthma Control Test (ACT), the STOP-BANG Score (for obstructive sleep apnea), and the Newcastle Laryngeal Hypersensitivity Questionnaire (a measure of laryngeal symptoms).
- Mallampati score will be calculated by looking into the subject's mouth and neck circumference will be measured by using a disposable paper measuring tape.

- No data will be obtained or accessed from the medical record.
- Oscillometry will be performed as follows:
 - A new disposable mouthpiece/filter will be attached to the device.
 - A noseclip will be provided and can be self-applied by the subject.
 - The subject will then place mouth over the mouthpiece.
 - The subject will place hands over cheeks to limit upper airway artifact.
 - The subject is asked to breath normally.
 - The investigator will then press the button on the side of the device to begin data collection.
 - One run of the test is about 20-30 seconds of tidal breathing. The test will be repeated at least 3 times to ensure repeatability.
 - The subject will then be instructed to rest off of the mouthpiece and nose clips will be removed.
 - Next, the subject will be instructed to take five sequential deep breaths to maximal lung inflation (TLC) and maximal lung deflation (RV). Subjects will be encouraged to achieve maximal values (e.g. “keep going!” during inhalation, and “blow, blow blow!” during exhalation).
 - Then oscillometry will be repeated as above.
 - Once testing has concluded, the removable mouthpiece/filter will be discarded into a biohazard bin. The device and all surfaces will be wiped down with a Cavi Wipe or a Hydrogen Peroxide Wipe.

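### A test at p<0.05 after 20 subjects, with a loosely defined option to add 20, gives an error per outcome of about 5.9% to at most 8.4% if 0.05 is reused on the pooled 40

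*Protocol*

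**What the plan says.** The rule is in the data analysis plan at the end of Section 16 of the protocol.

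- **Threshold:** "Statistical significance will be determined as" p < 0.05. No other threshold appears.
- **First look:** "Differences between Pre and Post values will be analyzed after the first twenty (20) subjects have completed testing".
- **Extension:** "If promising trends appear with borderline significance", with 0.05 to 0.10 as an example, "or if there are a subset of apparent responders, then an additional twenty subjects will be enrolled and analyzed".
- **Test:** "Differences between Pre and Post will be determined using t-test or ANOVA". Pairing is not mentioned.

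Three other sections bear on how this is read. Section 8 measures each subject, has the subject take five deep breaths, and then states "Then oscillometry will be repeated as above", so the data are paired by design. Section 13 states "The investigators will otherwise include all data collected from subjects who undergo the proper consent process and who are able to perform the test", which suggests that a second analysis would use all 40. Section 4.1 states "Up to fifty (50) healthy subjects will be recruited", although 20 plus 20 reaches only 40.

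**The concern.** A second test that depends on the result of the first gives chance another opportunity to produce p<0.05. If the same threshold is used both times and success at either counts, the error rate is above 5%. Here the size of the excess cannot be fixed in advance. The borderline band is only an example, and the responder trigger has no stated size, direction, number of subjects or outcome. The plan also leaves open which threshold applies at the second analysis, whether the 40 are pooled, and whether a significant 20-subject result survives an extension.

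The Pre-Post comparison is the study's only inferential aim, although Section 2 calls it secondary to gaining experience with the device. Section 15 foresees sharing results at conferences. Section 2 also links a reliable effect in healthy subjects to later asthma research, so a false positive could misdirect that work. With an undefined responder trigger, the true error rate could not be recovered afterwards.

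**Working it through.** The protocol gives no power or overall error figure to reproduce; its only design figure is p<0.05.

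**Inputs from Section 16:** threshold 0.05, first look at 20, extension by 20, example band 0.05 to 0.10, outcomes Rrs, Xrs and Fres.

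**Assumptions:** two-sided test; paired (from Section 8); 40 pooled (from Section 13); 0.05 reused; a significant first look stands.

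**Step 1, normal theory, one outcome.** Let Z1 be the statistic at 20 and Z2 the pooled statistic at 40. With no effect, their correlation is √(20/40) = 0.707. If the study extends when |Z1| lies between L and 1.960, then

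error = 0.05 + P(L < |Z1| < 1.960 and |Z2| > 1.960).

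- Own p of 0.05 to 0.10 extends (L = 1.645): 0.05 + 0.0082 = 0.0582.
- Every non-significant first look extends (L = 0): 0.05 + 0.0331 = 0.0831.
- In between: extending up to p<0.20 gives 6.8%, and up to p<0.50 gives 7.8%.

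**Step 2, paired t-tests (19 and 39 degrees of freedom), 60 million simulated trials.** First look alone 5.00%; own band 5.85%; always extended 8.39%. The last figure is the upper bound for any responder rule on this reading.

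**Step 3, three outcomes sharing one extension** (assumed correlation 0, 0.5 and 0.8; 1,000,000 trials each). Error per outcome is 5.83% to 5.88% for the own band, 6.13% to 6.18% if a borderline p on any outcome extends, and 8.37% to 8.41% if always extended.

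**Step 4, other readings of the same text.**

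| Reading | Error per outcome |
|---|---|
| Second 20 tested alone, own band | 0.05 + 0.05 × 0.05 = 5.25% |
| Second 20 tested alone, always extended | 1 − 0.95² = 9.75% |
| Pooled 40 replaces first look, own band only | 5.85%, as in Step 2 |
| Pooled 40 replaces first look, band on any outcome | 5.0% to 5.8% |
| Pooled 40 replaces first look, band plus one of three assumed responder rules | 4.6%, 4.9%, 5.5% |
| Unpaired t-test, assumed Pre-Post correlation 0.5, first look stands | 0.9% to 1.3% |

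The three assumed responder rules, in the order shown, are at least 4 subjects changing by more than 1 SD in the same direction, at least 3 by more than 1 SD, and at least 2 by more than 1.96 SD.

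The third row equals Step 2 because a significant first look is never extended when only the outcome's own borderline p can extend it. Which analysis counts matters only when another outcome or the responder trigger causes the extension.

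**The case against.** The strongest case on the other side has five parts.

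1. **Size.** The only numeric trigger gives 5.9%, an excess of about 0.9 points. The 8.4% needs every non-significant first look to be extended, which the text does not say. This stands: 8.4% is a bound. But an undefined responder trigger permits no tighter one.
2. **Dependence on assumptions.** Other readings give about 5%, or about 1%. This also stands, and it supports the point: one written rule should not cover rates from about 1% to nearly 10%. The near-5% reading also offers no escape when only the outcome's own p extends the study.
3. **Detail that a separate statistical analysis plan may supply.** The protocol itself writes the threshold, the first look and the extension rule. A plan written after the first 20 results are known could not cleanly repair them.
4. **Exploratory, low-risk study.** This lowers the severity. The label is given as the reason for having no power calculation; it does not withdraw the declaration of significance at 0.05. Labelling the p-values exploratory and reporting both looks would be lighter, but would leave that declaration with no defined error rate.
5. **Three outcomes are a larger source of error.** True: with independent outcomes, a single look already gives 1 − 0.95³ = 14.3% for any false positive. That is a separate matter, which the remedy here does not address.

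**Conclusion.** The concern holds. With a two-sided paired test, 0.05 reused on the pooled 40 and a significant first look standing, error per outcome is about 5.9% from the outcome's own borderline band. It is 6.1% to 6.2% if any outcome's borderline p extends, and at most 8.4% under any responder rule. None of those conditions is written down, and the result changes with each. The inflation is modest and the study exploratory, so this should be fixed but does not threaten the study.

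**What to change.** Keep the optional extension and amend the data analysis plan in Section 16 to state that:

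- the test is paired, on within-subject Pre-Post differences;
- the second analysis pools all 40 subjects and is the last one;
- significance is p<0.0294 at both the 20-subject and the pooled 40-subject analysis;
- the borderline band is 0.0294 to 0.10, since otherwise a p of 0.0294 to 0.05 is neither significant nor a reason to extend;
- any look at responders is reported as descriptive only.

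**Effect on error.** The value 0.0294 is the common threshold a solving a + P(|Z1| < c and |Z2| > c) = 0.05, where c is the two-sided normal cut-off for a. With paired t-tests, error per outcome is 3.8% if that outcome's own p<0.10 extends, 4.1% if any outcome's p<0.10 extends, and 5.1% if every first look is extended. The responder trigger therefore need not be removed. The last-analysis statement matters because Section 4.1 allows 50 subjects. The protocol plans no look at 50, but an added one would raise the error at 0.0294 to as much as 6.3%.

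**Cost.** Only wording changes; the enrolment ceiling is unaffected. The effect detectable with 80% power, in SDs of the within-subject change, rises from 0.66 to 0.72 at 20 subjects and from 0.45 to 0.49 at 40. With p-triggered extension only, power over both looks goes from 68% to 66% at a true effect of 0.5 SD, and stays at about 88% at 0.66 SD. Without the band reset it would fall to 58% and 80%. More first looks will be extended, because a p of 0.0294 to 0.05 then leads to 20 more subjects instead of a claim.
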